Drugs of abuse	X										
Alcohol and cotinine tests ⁴	X										
Brief Physical Exam		X								X	
Laboratory safety tests	X	X		X					X	X	
12-lead ECG	X	X	X ⁵	X					X	X	
Vital signs (HR and BP)	X	X	X ⁵	X					X	X	
Oral dose			X								
Blood samples for total radioactivity, [¹⁴ C]-GSK2269557 analysis and cold GSK2269557 analysis		X ⁶	X	X	X	X	X		X		
Blood samples for metabolite profiling		X	X ⁷	X							
Urine collection ^{8,9}		X	X	X	X	X	X	X	X		
Faecal collection ^{10,11}		X ¹¹	X	X	X	X	X	X	X	X ¹²	
Meals ¹³			X								

Procedure	Treatment Period 2 (Oral dosing)									Follow-up (7-14 days post-last dose) ^{2,3}	
	Day										
	-1	1 ¹	2	3	4	5	6	7	8		
AE/concomitant medication review ¹⁴		←	→								

1. There will be a washout of at least 14 days between dosing in treatment period 1 and 2.
2. If less than 1% of the dose is excreted in each 24 h period on Day 6 (120-144 h) and Day 7 (144-168 h) for a given participant, the participant may be discharged as early as Day 8 (after the LSC results are available), and no further samples (apart from for laboratory safety tests) will be collected. Follow-up procedures may be done at discharge and procedures scheduled for Day 8 and follow up will only be done once.
3. If excretion is higher than 1%, or if the results are inconclusive in each 24-h period on Day 6 (120-144 h) and Day 7 (144-168 h) for a given participant, that participant will remain at the unit, and urine and faecal collections will continue at 24-h intervals, for up to 7 days (until the morning of Day 15), until excretion is less than 1%. All remaining participants will be discharged from the unit on Day 15. Follow-up procedures may be done at discharge. In the unlikely event that excretion is still higher than 1% upon discharge on Day 15, participants will continue to collect faecal samples only, at home, at 24-h intervals. Samples collected at home will be returned to the clinic every 2-3 days.
4. Breath test will be performed to check alcohol consumption. Both CO breath tests and urine cotinine tests will be performed to check smoking state.
5. Vital signs and ECG will be taken 6 h post dose.
6. Sampling times relative to the oral dose. Blood samples for total radioactivity, [¹⁴C]-GSK2269557 analysis and cold GSK2269557 analysis will be taken: pre-dose and at 0.25, 0.5, 0.75, 1, 2, 3, 4, 6, 8, 10, 12, 16, 24, 48, 72, 96 and 168 h post-dose.

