7.1. Treatments Administered

Study treatment			
Study Treatment Name:	[¹⁴ C]-GSK2269557 solution for IV infusion	GSK2269557 Ellipta DPI	[¹⁴ C]-GSK2269557 oral solution
Dosage formulation:	[¹⁴ C]-GSK2269557 hemisuccinate salt (GSK2269557T) in normal saline	GSK2269557 hemisuccinate salt (GSK2269557H) blended with lactose and magnesium stearate ¹ packed in foil blisters	[¹⁴ C]-GSK2269557 hemisuccinate salt (GSK2269557T) in water
Unit dose strength(s)/ Dosage level(s):	10 µg [¹⁴ C]-GSK2269557 (<0.5 µCi) in 10 mL	500 µg GSK2269557 per inhalation / 1000 µg dose	800 µg [¹⁴ C]-GSK2269557 (approximately 50 µCi) in 10 mL
Route of Administration:	IV infusion	Oral Inhalation	Oral
Dosing instructions:	Non-sterile powder is to be dissolved aseptically in 0.9% sodium chloride v/w to a concentration of 1 µg/mL free base equivalent. IV solution is prepared by sterile filtration. 20 mL will be withdrawn into Individual labelled participant specific 60 mL syringes. Only 10 mL of IV solution, equivalent to 10 µg GSK2269557 is then administered intravenously as a single dose over 15 minutes, as soon as possible (within 5 minutes) after the start of the inhaled dose	Inhale TWICE from this Inhaler, as directed.	Non-sterile powder is to be dissolved in sterile water to a concentration of 80 µg/mL. 10 mL of the solution, equivalent to 800 µg, is then administered as a single oral dose. Participants can have up to 250 mL water to wash the dose down
Packaging and Labelling	Labelled drug substance will be provided in High Density Polyethylene (HDPE) containers with polypropylene closure to the site pharmacy.	Study Treatment will be provided in a foil overwrap. Each foil overwrap will be labelled as required per country requirement.	Labelled drug substance will be provided in HDPE containers with polypropylene closure to the site pharmacy.
Manufacturer	GSK	GSK	GSK
Device:		ELLIPTA™ inhaler	

1. Magnesium stearate 0.4% w/w of total drug product

For more information on the preparation of the oral and IV dosing solutions, please refer to the Study Reference Manual (SRM).

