### 11.3. Appendix 3: Study Phases and Treatment Emergent Adverse Events

#### 11.3.1. Study Phases

Assessments and events will be classified according to the time of occurrence relative to the start and/or stop time/date of the study treatment within the period (for period 1 the inhaled and IV dose, for period 2 the oral dose).

These treatment phases are already defined in the Time and Event table in [Appendix 2 Schedule of Activities](#) (Section [11.2](#)).

Treatment Phase	Definition
Pre-Treatment	Date/Time ≤ Study Treatment Start Date/Time
On-Treatment	Study Treatment Start Date/Time < Date/Time ≤ Study Treatment Stop Date/Time
Post-Treatment	Date/Time > Study Treatment Stop Date /Time

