### 11.3.2. Treatment Emergent Flag for Adverse Events

Flag	Definition
Treatment Emergent	

• If AE onset date is on or after treatment start date & on or before treatment stop date plus washout.

• Study Treatment Start Date <math>\leq</math> AE Start Date <math>\leq</math> Study Treatment Stop Date + 14 days.

• For studies with greater than one treatment period (e.g., crossover study), if AE onset is during one period and worsens during a later period it would be counted in both periods. For the initial period the logic would be as above. For the later period the logic would use the treatment dates associated with the later period:

• Treatment Period Start Date <math>\leq</math> AE Worsening Date <math>\leq</math> Study Treatment Stop Date +14 days.

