**NOTES:**

- If the study treatment stop date is missing, then the AE will be considered to be On-Treatment.
- Time of study treatment dosing and start/stop time of AEs should be considered, if collected.

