### 11.5.2. Study Population

Study Population
Age

 
GSK standard IDSL algorithms will be used for calculating age where birth date will be imputed as follows: 
 
Any subject with a missing day will have this imputed as day '15'.
 
Any subject with a missing date and month will have this imputed as '30th June'.
 
The year of the birth date will be captured in the pCRF
 
 
 
 
Age will then be derived as the integer value of [(DoB- date of Screening)/365.25]
 
 
Birth date will be presented in listings as 'YYYY'.
 

Body Mass Index (BMI)

 
Calculated as Weight (kg) / [Height (m) 2]
 

Treatment Compliance

 
Treatment compliance will be calculated based on the formula:  <math display="block">\text{Treatment Compliance} = \text{Number of Actual Doses} / (\text{Planned Treatment Duration in Days} * \text{Frequency})</math> 
 
Frequency is 2 for BID and 1 for QD. Treatment compliance could be greater than 100% if there are events of overdose. Cumulative compliance (since Day 1) at each visit will be calculated.
 
Planned Treatment Duration is defined as 1 day in period 1 and 1 day in period 2.
 

Extent of Exposure

 
Number of days of exposure to study drug will be calculated based on the formula:
 

Study Population
Duration of Exposure in Days = Treatment Stop Date – (Treatment Start Date) + 1

 
Participants who were randomized but did not report a treatment start date will be categorised as having zero days of exposure.
 
The cumulative dose will be based on the formula: Cumulative Dose = Sum of (Number of Days x Total Daily Dose)
 
If there are any treatment breaks during the study, exposure data will be adjusted accordingly.
 

11.5.3. Safety

ECG Parameters
RR Interval

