	
 
If fully or partially missing dates are available following DBF, the following conventions will be applied for calculating the time to onset and the duration of the event:
 
 
Partially Missing Dates:
 
 
Missing Start Day: First of the month will be used unless this is before the start date of study treatment; in this case the latest study treatment start date will be used and hence the event is considered On-treatment as per Appendix 3 Study Phases and Treatment Emergent Adverse Events.
 
Missing Start Month: January will be used unless this is before the start date of study treatment; in this case the month of the latest study treatment start date will be used and hence the event is considered On-treatment as per Appendix 3 Study Phases and Treatment Emergent Adverse Events.
 
Missing Start Year: Current year will be used unless this is before the start date of study treatment; in this case the year of the latest study treatment start date will be used and hence the event is considered On-treatment as per Appendix 3 Study Phases and Treatment Emergent Adverse Events.
 
Missing Stop Day: Last day of the month will be used, unless this is after the stop date of study treatment; in this case the latest study treatment stop date will be used.
 
Missing Stop Month: December will be used, unless this is after the stop date of study treatment; in this case the latest month of study treatment stop date will be used.
 
Missing Stop Year: Current year will be used, unless this is after the stop date of study treatment; in this case the latest year of study treatment stop date will be used.
 
 
Fully Missing Dates:
 
Completely missing start or end dates will remain missing, with no imputation applied. Consequently, time to onset and duration of such events will be missing.

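### At the minimum 14-day washout, a new AE on the oral dosing day meets both regimens' treatment-emergent windows, and three SAP rules disagree on an onset at dose start

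*SAP*

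**What the plan says.** **Treatment-emergent flag.** SAP section 11.3.2 counts an AE whose onset date is no earlier than the treatment start date and "on or before treatment stop date plus washout". The next line gives the upper limit as "Study Treatment Stop Date + 14 days". Both limits are inclusive and written in dates. An AE is to be counted in both periods only if it begins in one and worsens in a later one. A note adds: "Time of study treatment dosing and start/stop time of AEs should be considered, if collected". A second note classes an AE as On-Treatment when the treatment stop date is missing.

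**Study phases.** SAP section 11.3.1 applies its phases within each period. Pre-Treatment is "Date/Time ≤ Study Treatment Start Date/Time", On-Treatment is after start and up to stop, and Post-Treatment is anything later.

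**Partial AE dates.** For some incomplete start dates, SAP section 11.6.2.1 says "in this case the latest study treatment start date will be used and hence the event is considered On-treatment", and cites Appendix 3 (section 11.3) as its authority.

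**Dosing.** Protocol section 2, Period 2 schedule, footnote 1: "There will be a washout of at least 14 days between dosing in treatment period 1 and 2". Protocol section 7.1 says the oral solution "is then administered as a single oral dose". SAP section 11.5.2: "Planned Treatment Duration is defined as 1 day in period 1 and 1 day in period 2".

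**The concern.** Safety after the IV, oral and inhaled doses is a secondary objective, and the SAP reports data by treatment received. Section 11.3 holds the SAP's timing rules for tying an event to a period. Two things go wrong there.

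- The Period 1 window has the same length as the shortest permitted washout and includes its last day. That day can be the oral dosing day, and no rule assigns a new-onset AE on it to one regimen.
- The phase definitions suit a course of treatment better than a single administration. They classify an event at dose start differently in different sections. This is foreseeable, because protocol section 3.3.1 reports cough immediately after inhaled dosing in previous studies.

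At stake are an AE duplicated under the inhaled + IV regimen, and phase labels that two programmers could derive differently from the same record.

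**Working it through.** **Inputs**

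- Window: start date ≤ onset ≤ stop date + 14 days (SAP 11.3.2).
- Interval between doses, *w*: at least 14 days (Protocol section 2).
- The infusion starts within 5 min of the start of the inhaled dose (Protocol section 2, Period 1 footnote 4) and lasts 15 min (section 5.1.2).
- There is one oral dose, so its start and stop coincide (Protocol 7.1).
- Six participants (Protocol 5.2).

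**1. The plan's own figure.** The 14 days in 11.3.2 equal the protocol's minimum washout. The two ways of writing the upper limit, plus washout and + 14 days, therefore agree only when *w* = 14.

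**2. By date.** Call the Period 1 dosing day day 0. The Period 1 window is days 0 to 14, and the oral window is days *w* to *w* + 14.

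| *w* | Oral window | Days in both windows | Days before the oral dose in neither |
|---|---|---|---|
| 14 | 14–28 | day 14 | none |
| 15 | 15–29 | none | none |
| 16 | 16–30 | none | day 15 |
| 21 | 21–35 | none | days 15–20 |

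The overlap is one whole day, and occurs only at *w* = 14. For *w* above 15, *w* − 15 dates carry no treatment-emergent flag.

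**3. By clock time.** Period 1 treatment ends at most about 5 + 15 = 20 min after inhalation starts, so its window closes at 14 days + 20 min.

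- Oral dose at the same clock time as the inhaled dose, 14 days later: overlap 20 min.
- Fourteen days counted from the end of infusion: overlap at most a single instant.
- Oral dose on day 14 but one hour earlier by the clock: 60 + 20 = 80 min.

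**4. Phases.** On-Treatment is start < t ≤ stop.

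- Oral dose: start = stop, so no t qualifies. A completely timed event goes from Pre-Treatment at t = start directly to Post-Treatment.
- Period 1: the interval is at most about 20 min by clock time, and empty by date.
- By date alone, any AE on a dosing day has t = start, so it is Pre-Treatment in 11.3.1 and treatment-emergent in 11.3.2.
- An AE date imputed to treatment start is On-treatment in 11.6.2.1, citing Appendix 3, while 11.3.1 in that appendix makes it Pre-Treatment.

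**5. Size.** One participant in six is 1/6 = 16.7 percentage points. That is how far a Period 1 AE incidence rises if one participant's oral-day event is also counted there and he has no other Period 1 event in that row.

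**The case against.** The case for leaving the text alone has substance.

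- **Clock times.** The SAP already calls for times if collected, and protocol section 7.6 records dose times. With AE times as well, almost all of the overlap goes. Protocol sections 1 and 5.1.2 place the washout after both inhaled and IV dosing; counted from the end of infusion, only an instant remains. This stands, but neither document says whether AE times are collected.
- **Phase labels.** A reader might infer that no event can ever be On-Treatment for the oral dose. That goes too far: the missing-stop-date note and the imputation rule in 11.6.2.1 each place some incomplete records there. The set is empty only for completely dated events. The imputation rule is also a fallback, since partial AE dates go first to data management.
- **Late events.** A reader might infer that AEs after day 14 and before the oral dose are lost. They are not. Post-Treatment has no upper limit, and Table 3.1 and Listing 13 are titled as covering all AEs. Such events lack only the treatment-emergent flag. A 14-day cap is a legitimate choice, and + 14 days may simply put a number on the washout. The documents state no maximum interval between doses, so no upper bound on the unflagged days can be given.
- **Outputs.** No Appendix 9 title is defined by these flags, and the SAP plans no treatment comparisons. This limits the impact, but does not reconcile rules that contradict each other.

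**Conclusion.** The point holds in limited form. By date, and at an interval of exactly 14 days, the SAP's rule places a new AE on the oral dosing day in both regimens' windows, contrary to its own intention on double counting. This matters mainly if AE times are missing or not collected. With times, and both doses at the same time of day, the overlap is about 20 min at most. Independently of that, sections 11.3.1, 11.3.2 and 11.6.2.1 give three different classifications to an onset equal to treatment start, and On-Treatment is empty for a completely dated event around the oral dose.

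The 16.7 percentage points apply only to a participant dosed at exactly 14 days who has a new AE on that day. The event would be duplicated, not removed from the oral regimen. A reader might infer that the AE tables will be wrong. The documents do not show this: Tables 3.1 to 3.4 do not mention treatment emergence in their titles, and all AEs are listed individually.

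The conclusion assumes that start and stop dates in 11.3.2 are those of the period, as 11.3.1 says. A study-level reading would give no attribution by regimen at all.

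**What to change.** Amend the SAP as follows.

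1. End the Period 1 treatment-emergent window at the earlier of stop + 14 days and the start of the oral dose.
2. Assign a new-onset AE at or after the oral dose start to the oral regimen only. Keep the rule that an AE worsening in Period 2 counts in both periods.
3. Classify an onset equal to dose start as post-dose, and say that this also applies when only the date is known.
4. Replace or drop the On-Treatment phase for single doses, and bring 11.3.1, the missing-stop-date note under 11.3.2 and 11.6.2.1 into line with that.
5. Make the two statements of the upper limit in 11.3.2 agree. Whether to keep the 14-day cap when the washout is longer is the sponsor's choice. Keeping it leaves some dates unflagged. Removing it gives participants windows of unequal length and attributes later events to a single dose.

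The cost is SAP wording and one programming rule. No data collection changes.

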**NOTES:**

- If the study treatment stop date is missing, then the AE will be considered to be On-Treatment.
- Time of study treatment dosing and start/stop time of AEs should be considered, if collected.

## 11.4. Appendix 4: Data Display Standards & Handling Conventions

### 11.4.1. Reporting Process

Software	

 
The currently supported versions of SAS software will be used.
 
	
Reporting Area	
HARP Server	: UK1SAL00175
HARP Compound	: GSK2269557
HARP Study	: mid206764
Analysis Datasets	

 
Analysis datasets will be created according to Clinical Data Interchange Standards Consortium (CDISC) standards. If the Study Data Standardization Plan (SDSP) exists for a study, ensure the CDISC versions are consistent.
 
	
Generation of RTF Files	

 
RTF files will be generated for summary tables.
 
	

### 11.4.2. Reporting Standards

General	

 
The current GSK Integrated Data Standards Library (IDSL) will be applied for reporting, unless otherwise stated (IDSL Standards Location: https://spope.gsk.com/sites/IDSLLibrary/SitePages/Home.aspx):           
 
4.03 to 4.23: General Principles
 
5.01 to 5.08: Principles Related to Data Listings
 
6.01 to 6.11: Principles Related to Summary Tables
 
7.01 to 7.13: Principles Related to Graphics
 
 
 
Do not include subject level listings in the main body of the GSK Clinical Study Report. All subject level listings should be located in the modular appendices as ICH or non-ICH listings
 
	
Formats	

 
All data will be reported according to the actual treatment the subject received unless otherwise stated.
 
GSK IDSL Statistical Principles (5.03 & 6.06.3) for decimal places (DP's) will be adopted for reporting of data based on the raw data collected, unless otherwise stated.
 
Numeric data will be reported at the precision collected on the pCRF.
 
The reported precision from non pCRF sources will follow the IDSL statistical principles but may be adjusted to a clinically interpretable number of DP's.
 
	
Planned and Actual Time	

 
Reporting for tables, figures and formal statistical analyses:           
 
Planned time relative to dosing will be used in figures, summaries, statistical analyses and calculation of any derived parameters, unless otherwise stated.
 
The impact of any major deviation from the planned assessment times and/or scheduled visit days on the analyses and interpretation of the results will be assessed as appropriate.
 
 
 
Reporting for Data Listings:           
 
Planned and actual time relative to study drug dosing will be shown in listings (Refer to IDSL Statistical Principle 5.05.1).
 
Unscheduled or unplanned readings will be presented within the subject's listings.
 
 
 
	

Unscheduled Visits	

 
• Unscheduled visits will not be included in summary tables and/or figures.
 
• All unscheduled visits will be included in listings.
 
	
Descriptive Summary Statistics	
Continuous Data	Refer to IDSL Statistical Principle 6.06.1
Categorical Data	N, n, frequency, %
Graphical Displays	

 
• Refer to IDSL Statistical Principles 7.01 to 7.13.
 
	

### 11.4.3. Reporting Standards for Pharmacokinetic

Pharmacokinetic Concentration Data	
PC Windows Non-Linear (WNL) File	PC WNL file (CSV format) for the non compartmental analysis by Clinical Pharmacology Modelling and Simulation function will be created according to PKOne. Note: Concentration values will be imputed as per GUI_51487
Descriptive Summary Statistics, Graphical Displays and Listings	Refer to IDSL PK Display Standards. Refer to IDSL Statistical Principle 6.06.1. Note: Concentration values will be imputed as per GUI_51487 for descriptive summary statistics/analysis and summarized graphical displays only.
Pharmacokinetic Parameter Derivation	
Plasma PK Parameter to be Derived by Programmer	The following PK parameters will be derived by the Programmer: CL r , ML(iv), ML(po), F g , E H , F abs , F(Oral, (0-t)), F(Oral, (0-∞)), F(inhaled, (0-t)), F (inhaled, (0-∞)) and the Parent GSK2269557/ Total Radioactivity ratio for Cmax, AUC(0-t), AUC(0-24) and AUC(0-∞). note: Parent GSK2269557/ Total Radioactivity ratios will be either GSK2269557/ Total Radioactivity or [14C]-GSK2269557/ Total Radioactivity depending on the method of sample analyses and are of interest for the radiolabelled IV and oral dose.
Urine and Faeces PK Parameter to be Derived by Programmer	The following PK parameters will be derived by the Programmer: cumulative Ae, Fe% and cumulative Fe%.
Pharmacokinetic Parameter Data	
Is NQ impacted PK Parameters Rule Being Followed	No.
Descriptive Summary Statistics, Graphical Displays and Listings	Refer to IDSL PK Display Standards. Refer to PKOne

## 11.5. Appendix 5: Derived and Transformed Data

### 11.5.1. General

Multiple Measurements at One Analysis Time Point

 
Triplicate measures of 12-lead ECG and vital signs (HR and BP) will be taken at screening and pre dose for period 1. The mean of the measurements will be calculated and used in any derivation of summary statistics but if listed all data will be presented.
 
There are no other scheduled multiple measurements however, if multiple measurements are recorded at a given time point the following process will be followed: 
 
[1] Mean of the measurements will be calculated and used in any derivation of summary statistics but if listed, all data will be presented.
 
[2] If there are two values within a time window (as per Section 11.2) the value closest to the target day for that window will be used. If values are the same distance from the target then the mean will be taken.
 
[3] Subjects having both High and Low values for Normal Ranges at any post-baseline visits for safety parameters will be counted in both the High and Low categories of "Any visit post-baseline" row of related summary tables. This will also be applicable to relevant Potential Clinical Importance summary tables.
 
 
 

Study Day

 
Calculated as the number of days from First Dose Date: 
 
Ref Date = Missing → Study Day = Missing
 
Ref Date < First Dose Date → Study Day = Ref Date – First Dose Date
 
Ref Date ≥ First Dose Date → Study Day = Ref Date – (First Dose Date) + 1
 
 
 

